1.0 TRIAL SUMMARY

Abbreviated Title	RadVax™: Pembrolizumab & Hypofractionated Radiotherapy
Phase	Phase I
Clinical Indication	Metastatic cancers
Trial Type	Phase I cohort with randomized expansion phase
Type of control	N/A
Route of administration	i.v.
Trial Blinding	N/A
Treatment Groups	2 radiotherapy cohorts; 5 disease cohorts
Number of trial subjects	70
Estimated duration of trial	2 years
Duration of Participation	3 months

IRB #: 821403

UPCC#: 40914

Original Version: February 3, 2015

This document is a protocol for a human research study. This study is to be conducted according to US and international standards of Good Clinical Practice (FDA Title 21 part 312 and International Conference on Harmonization guidelines), applicable government regulations and Institutional research policies and procedures.

2.0 TRIAL DESIGN

2.1 Trial Design

This is a Phase I cohort study of a fixed dose of Pembrolizumab in combination with two distinct regimens of hypofractionated radiotherapy. There will be five groups of patient diagnoses:

- Metastatic melanoma patients who have progressed while on PD-1 or PDL-1 therapy
- Metastatic NSCLC patients who have progressed while on PD-1 or PDL-1 therapy
- Metastatic & locally advanced pancreatic cancer patients
- Metastatic Breast cancer patients
- Other metastatic cancer patients

Pembrolizumab will be administered at a dose of 200 mg every 3 weeks beginning 7 days (+/- 3 days) prior to the first fraction of hypofractionated radiation and will continue for a total of 6 cycles. In the initial **Safety Phase**, there will be two cohorts of patients based upon the radiotherapy dose delivered to the index metastatic lesion in the lung, liver, bone or soft tissue:

Cohort 1: 8 Gy x 3 to the index lesion

[figure not shown]
Cohort 2: 17 Gy x 1 to the index lesion*

*Subjects with locally advanced pancreatic cancer will be enrolled only in the 8 Gy x 3 cohort.

Patients are stratified by prior PD-1 therapy. 24 patients will be enrolled, 12 per stratum and 6 per fractionation cohort. Standard safety decision-making will be used. The regimen is safe if 0-1 dose-limiting toxicities (DLT) in 6 patients (3 from each strata). Enrollment in a cohort will stop if 2+ DLT are observed within a cohort at any time during the safety phase. If 2+ DLT are observed in Cohort 1, then Cohort 2 will still be tested. Cohort 1 → Cohort 2 is **not** an escalation of dose. DLT is defined as any Grade 3 or higher non-hematological toxicity and any Grade 4 hematological toxicity that is probably, possibly or definitely related to the combination of Pembrolizumab and hypofractionated radiotherapy. The window in which DLTs will be recorded is from the first Pembrolizumab infusion to 35 days after the last radiation fraction.

In the **Expansion Phase**, patients will be stratified by disease site. If both fractionation regimens are safe, then we randomize patients. Otherwise, all patients will be enrolled on the single regimen determined to be safe. 46 patients will be enrolled. Randomization will aid in the preliminary assessment of clinical response by avoiding selection bias. Accrual is expected to occur over 24 months or 3-4 subjects per month.

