4.2.3 Rationale for Primary Endpoint

This is a Phase I study that will determine the safety of combining Pembrolizumab with hypofractionated radiotherapy. The absence of clinical data regarding the safety of this combination mandates the performance of a Phase I trial. The primary endpoint, therefore, will be the safe dose or doses of hypofractionated radiotherapy in combination with Pembrolizumab as defined by 0 or 1 DLTs observed in 6 patients within each radiation dose cohort.

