5.2 Trial Treatments

The treatment to be used in this trial is outlined below in Tables 2 and 3

Table 2 Pembrolizumab Treatment

Drug	Dose/Potency	Dose Frequency	Route of Administration	Regimen/Treatment Period	Use
Pembrolizumab	200 mg	Every 3 weeks	IV infusion	6 three week cycles*	Experimental
The PEMBROLIZUMAB dosing interval may be increased due to toxicity as described in Section 5.2.1.2.					

Pembrolizumab should be administered 7 days (+/- 3 days) prior to the first fraction of hypofractionated radiation.

*NOTE: Patients who have stable or responding disease and are felt to be clinically benefiting from the drug can continue receiving pembrolizumab for up to 2 years. For cancers not currently commercially approved for treatment with pembrolizumab, the drug will be provided by Merck.

In the initial ***Safety Phase***, there will be two cohorts of patients based upon the radiotherapy dose delivered to the index metastatic lesion in the lung, liver, bone or soft tissue:

Cohort 1: 8 Gy x 3 to the index lesion

Cohort 2: 17 Gy x 1 to the index lesion*

*Subjects with locally advanced pancreatic cancer will be enrolled only in the 8 Gy x 3 cohort.

Patients are stratified by prior PD-1 therapy. 24 patients will be enrolled, 12 per stratum and 6 per fractionation cohort within each stratum. Standard safety decision-making will be used. The regimen is safe if no more than 0-1 dose-limiting toxicities (DLT) are observed in 6 patients within a cohort within a stratum. Enrollment in a cohort within a stratum will stop if 2+ DLT are observed within that cohort at any time during the safety phase. If 2+ DLT are observed in Cohort 1 in a stratum, then Cohort 2 within that stratum will still be tested. Cohort 1 → Cohort 2 is **not** an escalation of dose. DLT is defined as any Grade 3 or higher non-hematological toxicity and any Grade 4 hematological toxicity that is probably, possibly or definitely related to the combination of Pembrolizumab and hypofractionated radiotherapy.

Table 3. Hypofractionated Radiotherapy

Safety Phase:

Stratify	Progressed on Prior PD-1 (Melanoma or NSCLC) No Prior PD-1 (Pancreas, Breast or Other)	Cohort 1: 8 Gy x 3 → Cohort 2: 17 Gy x 1		TOTAL
		Number of Patients	Number of Patients	
		6	6	12
		6	6*	12
TOTAL		12	12	24
* Breast or Other cancer patients only				

Expansion Phase

Disease	Randomize		Number of Randomized Patients
	Cohort 1: 8 Gy x 3	Cohort 2: 17 Gy x 1	
Melanoma	7	7	14
NSCLC	7	7	14
Pancreas	6	0	6*
Breast	3	3	6

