8.0 STATISTICAL ANALYSIS PLAN

This is a stratified phase I trial with 2 phases: a safety phase and an expansion phase.

Safety Phase: Pembrolizumab is fixed. Two radiotherapy fractionation schedules are tested: 8 Gy x 3 and 17 Gy x 1. Patients are stratified by prior PD-1 therapy. 24 patients will be enrolled, 12 per stratum and 6 per fractionation cohort.

Table 11

	Progressed on Prior PD-1 (Melanoma or NSCLC)	Cohort 1: 8 Gy x 3 Number of Patients	Cohort 2: 17 Gy x 1 Number of Patients	TOTAL
		6	6	

May 3, 2017

Confidential  Limited Access

Stratify	No Prior PD-1 (Pancreas, Breast or Other cancers)	6	6*	12
	TOTAL	12	12	24
	* Breast or Other cancer patients only			

Safety Phase Decision-making: Dose limiting toxicity (DLT) is defined in Sections 2.1 and 5.2. The regimen is considered safe if 0-1 DLTs are observed in 6 patients within a stratum. Stop if 2+ DLT at any time. If 2+ DLT in Cohort 1, then Cohort 2 will still be tested. Cohort 1 → Cohort 2 is not an escalation of dose.

Expansion Phase: Patients are now stratified by disease site.

- If both fractionation regimens are considered safe for both prior PD-1 therapy strata, then we will randomize patients. Randomization will aid in our preliminary assessment of clinical response by avoiding selection bias. Although unlikely, if only one of the fractionation regimens is considered safe for both prior PD-1 therapy strata, then all patients will be enrolled on the fractionation regimen which was determined to be safe.

Table 12

Disease	Randomize		Number of Randomized Patients
	Cohort 1: 8 Gy x 3 Number of Patients	Cohort 2: 17 Gy x 1 Number of Patients	
Melanoma	7	7	14
NSCLC	7	7	14
Pancreas	6	0	6*
Breast	3	3	6
Other cancers	3	3	6
TOTAL	26	20	46
	* Pancreas patients are not randomized, they are assigned to 8 Gy x 3		

Expansion Phase Decision-making: We will first evaluate response rate by fractionation cohort. We will pool all disease sites. This is a global assessment of RADVAX™ by fractionation cohort. Of 38 patients in cohort 1, 26 (68%) and of 32 patients in cohort 2, 20 (63%) will have been randomized to treatment in the expansion phase, which strengthens any comparative conclusions, although preliminary. Immune PD markers will also be examined by fractionation cohort.

Table 13

	Cohort 1: 8 Gy x 3 Number of Patients	Cohort 2: 17 Gy x 1 Number of Patients	STUDY TOTAL
Safety phase	12	12	24
Expansion phase	26	20	46
TOTAL	38	32	70

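### The DLT rule behind the primary endpoint is stated on different patient units in Sections 2.1, 4.2.3, 5.2 and 8.0, so the same data can stop a cohort and pass it as safe

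*Combined protocol and SAP*

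**What the plan says.** The safety rule appears in four places in the combined protocol and SAP.

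- **Section 2.1 (Trial Design).** The size is given as "24 patients will be enrolled, 12 per stratum and 6 per fractionation cohort. Standard safety decision-making will be used". The safe rule reads "The regimen is safe if 0-1 dose-limiting toxicities (DLT) in 6 patients (3 from each strata"), and the stop rule reads "Enrollment in a cohort will stop if 2+ DLT are observed within a cohort at any time during the safety phase". The stop rule carries no stratum limit.
- **Section 4.2.3 (Rationale for Primary Endpoint).** A safe regimen is one with "0 or 1 DLTs observed in 6 patients within each radiation dose cohort". No stratum is named.
- **Section 5.2 (Trial Treatments).** The size becomes "24 patients will be enrolled, 12 per stratum and 6 per fractionation cohort within each stratum". The safe rule uses the same nested unit, and so does the stop rule: "Enrollment in a cohort within a stratum will stop if 2+ DLT are observed within that cohort at any time during the safety phase".
- **Section 8.0 (Statistical Analysis Plan).** "The regimen is considered safe if 0-1 DLTs are observed in 6 patients within a stratum". Each stratum has 12 safety patients, so the fractionation cohort is presumably implied. The accompanying stop rule at two or more DLTs names no unit.

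Tables 3 and 11 show four cells of six patients. Table 13 gives 12 safety patients per cohort.

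**The concern.** This rule defines the primary endpoint. It also decides whether the expansion phase randomizes between the two fractionations or assigns everyone to one. A threshold of at most one DLT means little until the denominator is fixed, and the documents give at least three: six patients per cohort (three per stratum), the whole cohort, and six per cohort within a stratum. If these can give opposite verdicts on the same patients, the primary endpoint has no single definition. The trial is open-label (Section 5.2.3), so a choice between readings could be made with the DLT counts in view. The chance of passing a toxic regimen, or rejecting a tolerable one, would then depend on which section was followed.

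**Working it through.** **Step 1: which unit reproduces the stated sample size.**

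- Two strata × two cohorts × 6 = 24 patients, 12 per cohort and 12 per stratum. This matches Tables 3, 11 and 13. It also matches the totals in Section 8.0: 38 − 26 = 12 in Cohort 1 and 32 − 20 = 12 in Cohort 2.
- Six per cohort with three from each stratum gives 2 × 6 = 12 patients, half the 24 stated in the same paragraph of Section 2.1.

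**Step 2: one data set, two verdicts.** Suppose a cohort has 1 DLT in 6 patients in the prior-PD-1 stratum and 1 in 6 in the other, so 2 in 12.

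- Section 2.1 stop rule: two DLTs in the cohort, so enrolment stops.
- Section 5.2: one DLT in six in each cell, so no stop and safe in both strata.
- Section 8.0: safe under its safe rule, if that is read per cohort within stratum as in Table 11. Its stop rule can be read either way.

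This step needs no modelling assumption.

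**Step 3: how far the rules differ.** The documents give no DLT rate or error rate for this rule. The true rates p below are assumptions, with independent patients and the same p in both strata.

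- Rule A, at most 1 of 6 per cohort: (1−p)^6 + 6p(1−p)^5
- Rule B, at most 1 of 12 (the Section 2.1 stop rule on the tabulated cohort size): (1−p)^12 + 12p(1−p)^11
- Rule C, at most 1 of 6 in each of the two strata: A²
- B and C disagree only when there is exactly one DLT in each stratum: [6p(1−p)^5]²

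Worked at p = 0.20:

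- A = 0.2621 + 0.3932 = 0.655
- B = 0.0687 + 0.2062 = 0.275
- C = 0.6554² = 0.430
- Disagreement = 0.3932² = 0.155, which equals C − B as it should.

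| True DLT rate | A: 6 per cohort | C: 6 per stratum, both pass | B: 12 per cohort | B stops, C safe |
|---|---|---|---|---|
| 10% | 0.886 | 0.785 | 0.659 | 0.126 |
| 20% | 0.655 | 0.430 | 0.275 | 0.155 |
| 30% | 0.420 | 0.177 | 0.085 | 0.092 |

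Over a wider range, the chance of disagreement per cohort is 5.4% at a 5% rate, 16.0% at 15% and 3.5% at 40%. Its maximum is at p = 1/6, where 6p(1−p)^5 = (5/6)^5 = 0.402 and the square is about 16%.

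**The case against.** The strongest reply is that the intent can be recovered. Section 5.2 states the nested unit in full for sample size, safe rule and stop rule. Tables 3 and 11 agree with it. Section 8.0 asks whether a regimen is safe for both prior-PD-1 strata, which presupposes a verdict within each stratum. Section 8.0 also repeats the short sample-size phrase of Section 2.1 directly above Table 11, so that phrase may be shorthand for the nested layout. On this view the outliers are the three-per-stratum parenthesis and the stop sentence in Section 2.1. This makes the nested unit a plausible guess, but no section is said to govern, and Section 4.2.3, which defines the primary endpoint, names no stratum.

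A second reply is that no sentence states a 12-patient rule. Read literally as six per cohort, the safe and stop rules of Section 2.1 are complementary and cannot clash with each other. But Section 2.1 itself places 24 patients in two cohorts, so 12 per cohort, and its stop rule counts DLTs anywhere in the cohort. Applying it to 12 patients is a literal reading. That Section 2.1 supports both A and B is part of the problem.

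Two points stand. The probabilities assume equal DLT rates in strata that differ in disease and prior treatment, so they are illustrative. And the plan never claims an error rate for this rule, so the lack of operating characteristics is not itself a contradiction.

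**Conclusion.** The concern holds. The decision threshold for the primary endpoint and for the expansion gate is contradictory as written: one DLT in each stratum of a cohort stops it under Section 2.1 and passes it under Section 5.2. The unit in the Section 2.1 safe rule also fails to reproduce that section's own 24 patients. Neither point depends on an assumed DLT rate.

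The practical size does depend on one. With equal rates in both strata, the stop-versus-safe conflict has a 9 to 16% chance in each cohort for true rates between 10 and 30%. At a 20% rate the chance of declaring a regimen safe ranges from 27 to 66% according to the section followed. This must be fixed, because the primary endpoint currently lacks a single definition.

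**What to change.** Use one unit of decision, for both the safe rule and the stop rule, in Sections 2.1, 4.2.3, 5.2 and 8.0. The choice of rule belongs to the sponsor. There are two consistent ways to write it:

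1. If the unit is the cohort within a stratum, rewrite Sections 2.1 and 4.2.3 to say so, remove the three-per-stratum parenthesis, and add the cohort to the safe rule and a unit to the stop rule in Section 8.0.
2. If a cohort-level stop is intended, write it in Sections 5.2 and 8.0 as a rule on 12 patients, and align Sections 2.1 and 4.2.3 with it.

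Only four cells of six reproduce the stated 24 patients and Tables 3 and 11, so a different layout would also need new numbers and tables. In either case, state the verdict for one DLT in each stratum of a cohort. A short table of the probability of declaring a regimen safe under the chosen rule would be a useful addition. If safety-phase decisions have already been taken, record which rule was applied.

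The cost is wording in four places and, if added, one small table. No extra patients or visits are needed.

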2.2 Trial Diagram

3.0 OBJECTIVE(S) & HYPOTHESIS(ES)

3.1 Primary Objective(s) & Hypothesis(es)

(1) **Objective:** To determine the safety of combining Pembrolizumab with hypofractionated radiotherapy in patients with advanced and metastatic cancers.

Hypothesis: Pembrolizumab will be safe and well tolerated in patients with advanced and metastatic cancers when combined with hypofractionated radiotherapy.

3.2 Secondary Objectives

Objective: To estimate the immune-related response rate in non-index metastatic lesions of the combination of Pembrolizumab and hypofractionated radiotherapy

3.3 Exploratory Objective

(1) **Objective:** To explore the immune pharmacodynamic changes after treatment with the combination of Pembrolizumab and hypofractionated radiotherapy

(2) **Objective:** To explore the relationship between PD-1 expression and response to Pembrolizumab and hypofractionated radiotherapy

4.0 BACKGROUND & RATIONALE

4.1 Background

Historically patients with metastatic disease from epithelial cancers have rarely been cured. The 5-year survival rates for patients diagnosed between 2004 and 2010 with

metastatic NSCLC, melanoma, and breast cancer are respectively 4%, 16%, and 25% (<http://seer.cancer.gov/statfacts/>). Pancreatic cancer, regardless of stage has a poor prognosis, with an overall survival rate of 6.7%. For patients with localized pancreatic cancer, survival is 25.8%, with regional disease 9.9% and with distant metastases 2.3%.

Hypofractionated radiotherapy for oligometastatic disease

Hypofractionated radiotherapy for metastatic disease is commonly delivered with stereotactic body radiotherapy (SBRT) in which several non-coplanar photon beams are used to treat a tumor with a high degree of conformality resulting in little dose to surrounding normal tissues. SBRT has proven to be an effective local treatment for small, localized tumors. Initially, it was integrated as an ablative approach with a goal of tumor sterilization in oligometastatic disease with minimal morbidity and good long-term clinical outcome in these highly selected patients (1-4). Our goal in this protocol is different; we propose to use hypofractionated radiotherapy, either with or without an SBRT technique, to irradiate a single lesion in the setting of immune checkpoint blockade with the hope of augmenting a systemic response.

Immunologic approaches to treating patients with advanced stage cancer

Due to these poor survival rates, many different approaches have been tried for patients with advanced stage cancers. In particular, recent studies have shown benefit from immunotherapy. T lymphocytes are prime mediators of tumor immunosurveillance. Several immune checkpoint receptors are expressed on T cells that downregulate the activity of these cells after they have been activated. Hence, inhibition of these regulatory molecules is a means of augmenting anti-tumor response. Cytotoxic T-lymphocyte antigen-4 (CTLA-4; CD152) is a cell-surface receptor that is expressed (within approximately 72 hours *in vitro*) on T-lymphocytes in response to the activation by interaction with APCs or pharmacologic stimulation of the T-cell receptor (5). CTLA-4 activation downregulates T-cell proliferation and cytokine secretion, effectively limiting the immune reactivity directed against a given antigen stimulus. Therefore, inhibition of CTLA4 using an antibody is a potential strategy to prevent downregulation of the immune response. In 2010 Hodi *et al.* published the first phase III randomized trial demonstrating a survival benefit in patients with metastatic melanoma treated with ipilimumab, a fully human monoclonal antibody (IgG1) that blocks CTLA-4 (6). Based on this trial the drug was approved for use by the FDA in March 2011 for patients with metastatic melanoma.

Another immunomodulatory receptor that has garnered a great deal of attention is Programmed Death-1 (PD-1). PD-1 signaling involves binding to several discrete ligands, including PD-L1 and PD-L2. PD-L1 is often expressed within the tumor microenvironment by cancer cells and macrophages whereas PD-L2 is expressed primarily on professional antigen presenting cells (5). PD-1 negatively regulates the effector phase of the T cell response after ligation of PD-L1 to the receptor. Antibodies that block the PD-L1/PD-1 interaction prevent the downregulation of the anti-tumor immune response, hence augmenting the cytotoxic function of tumor-specific T cells.

Several PD-1 inhibitors have been used in large clinical trials. PEMBROLIZUMAB is a highly selective, humanized monoclonal antibody (IgG4) that blocks PD-1. Its safety and efficacy (response rate of 38% by RECIST criteria) have been demonstrated in melanoma (7). Another PD-1 inhibitor, BMS-936558, was found to be safe and to yield response rates (by RECIST) of 18%, 28%, 27% respectively in patients with advanced stage non-small lung cancer, melanoma and renal cell carcinoma (8).

Hypofractionated radiotherapy and immune activation

The effectiveness of the immunologic strategy outlined above is contingent upon T-lymphocyte activation through interaction with the APC having already occurred. Therefore, the development of novel strategies that successfully “vaccinate” patients to their cancer near the time of the delivery of the immunomodulatory antibody is an important area of clinical research. One means of potentially increasing exposure of T cells to tumor antigen is to expose the tumors to a few large fractions of radiation (hypofractionated radiotherapy).

There is emerging evidence that radiotherapy (RT) can stimulate the immune response, by a variety of mechanisms such as increasing TLR4 expression on dendritic cells, increasing priming of T cells in draining lymph nodes, and increasing tumor cell antigen presentation by dendritic cells (reviewed in (9)). Recently Verbrugge *et al.* showed that radiotherapy can enrich tumors of functionally active, tumor-specific effector cells (10). Lee *et al.* demonstrated that the therapeutic effect with ablative hypofractionated radiotherapy on local tumor control required activation of CD8+ T- lymphocytes (11).

Hypofractionated radiation has also been shown to potentiate systemic response to immunomodulatory therapy. A single large dose of RT increased the effects of Flt-3 ligand administration on distant pulmonary metastases, an effect that was only seen in immunocompetent C57Bl/6 mice, not immunodeficient nude mice (12). Hypofractionated radiation has also been shown to amplify immune response to traditional vaccines (13). Additionally, there are pre-clinical data to suggest that CTLA-4 blockade along with ablative radiotherapy to an index lesion can prevent the growth of a tumor outside the irradiated field (abscopal effect) through an immune-mediated effect (14).

In addition to these pre-clinical data, Postow *et al.* reported a patient with metastatic melanoma having progressive disease while on ipilimumab therapy who then underwent a course of hypofractionated RT to a painful paraspinal mass. The patient received a dose of ipilimumab two months after RT, and then had radiologic imaging two months after this, which showed radiologic regression of disease in the irradiated site as well as in regions outside the radiation fields (15).

4.1.1 Pharmaceutical and Therapeutic Background

The importance of intact immune surveillance in controlling outgrowth of neoplastic transformation has been known for decades [1]. Accumulating evidence shows a correlation between tumor-infiltrating lymphocytes (TILs) in cancer tissue and favorable prognosis in various malignancies [2; 3; 4; 5; 6]. In particular, the presence of CD8+ T-cells and the ratio

of CD8+ effector T-cells / FoxP3+ regulatory T-cells seems to correlate with improved prognosis and long-term survival in many solid tumors.

The PD-1 receptor-ligand interaction is a major pathway hijacked by tumors to suppress immune control. The normal function of PD-1, expressed on the cell surface of activated T-cells under healthy conditions, is to down-modulate unwanted or excessive immune responses, including autoimmune reactions. PD-1 (encoded by the gene *Pdcd1*) is an Ig superfamily member related to CD28 and CTLA-4 which has been shown to negatively regulate antigen receptor signaling upon engagement of its ligands (PD-L1 and/or PD-L2) [7; 8]. The structure of murine PD-1 has been resolved [9]. PD-1 and family members are type I transmembrane glycoproteins containing an Ig Variable-type (V-type) domain responsible for ligand binding and a cytoplasmic tail which is responsible for the binding of signaling molecules. The cytoplasmic tail of PD-1 contains 2 tyrosine-based signaling motifs, an immunoreceptor tyrosine-based inhibition motif (ITIM) and an immunoreceptor tyrosine-based switch motif (ITSM). Following T-cell stimulation, PD-1 recruits the tyrosine phosphatases SHP-1 and SHP-2 to the ITSM motif within its cytoplasmic tail, leading to the dephosphorylation of effector molecules such as CD3 ζ , PKC θ and ZAP70 which are involved in the CD3 T-cell signaling cascade [7; 10; 11; 12]. The mechanism by which PD-1 down modulates T-cell responses is similar to, but distinct from that of CTLA-4 as both molecules regulate an overlapping set of signaling proteins [13; 14]. PD-1 was shown to be expressed on activated lymphocytes including peripheral CD4+ and CD8+ T-cells, B-cells, Tregs and Natural Killer cells [15; 16]. Expression has also been shown during thymic development on CD4-CD8- (double negative) T-cells as well as subsets of macrophages and dendritic cells [17]. The ligands for PD-1 (PD-L1 and PD-L2) are constitutively expressed or can be induced in a variety of cell types, including non-hematopoietic tissues as well as in various tumors [18; 19; 20; 13]. Both ligands are type I transmembrane receptors containing both IgV- and IgC-like domains in the extracellular region and contain short cytoplasmic regions with no known signaling motifs. Binding of either PD-1 ligand to PD-1 inhibits T-cell activation triggered through the T-cell receptor. PD-L1 is expressed at low levels on various non-hematopoietic tissues, most notably on vascular endothelium, whereas PD-L2 protein is only detectably expressed on antigen-presenting cells found in lymphoid tissue or chronic inflammatory environments. PD-L2 is thought to control immune T-cell activation in lymphoid organs, whereas PD-L1 serves to dampen unwarranted T-cell function in peripheral tissues [13]. Although healthy organs express little (if any) PD-L1, a variety of cancers were demonstrated to express abundant levels of this T-cell inhibitor. PD-1 has been suggested to regulate tumor-specific T-cell expansion in subjects with melanoma (MEL) [21]. This suggests that the PD-1/PD-L1 pathway plays a critical role in tumor immune evasion and should be considered as an attractive target for therapeutic intervention.

PEMBROLIZUMAB (previously known as SCH 900475) is a potent and highly selective humanized monoclonal antibody (mAb) of the IgG4/kappa isotype designed to directly block the interaction between PD-1 and its ligands, PD-L1 and PD-L2.

